Appendix B Adverse Event Definitions and Additional Safety Information

B 1 Definition of Adverse Events

An adverse event is the development of any untoward medical occurrence in a subject or clinical study subject administered a medicinal product and which does not necessarily have a causal relationship with this treatment. An AE can therefore be any unfavourable and unintended sign (e.g., an abnormal laboratory finding), symptom (for example nausea, chest pain), or disease temporally associated with the use of a medicinal product, whether or not considered related to the medicinal product.

The term AE is used to include both serious and non-serious AEs and can include a deterioration of a pre-existing medical occurrence. An AE may occur at any time, including screening or washout periods, even if no Study treatment has been administered.

B 2 Definitions of Serious Adverse Event

A serious adverse event is an AE occurring during any study phase (i.e., screening, treatment, follow-up), that fulfils one or more of the following criteria:

- Results in death
- Is immediately life-threatening
- Requires in-subject hospitalisation or prolongation of existing hospitalisation
- Results in persistent or significant disability or incapacity
- Is a congenital anomaly or birth defect
- Is an important medical event that may jeopardise the subject or may require medical treatment to prevent one of the outcomes listed above

B 3 Life Threatening

'Life-threatening' means that the subject was at immediate risk of death from the AE as it occurred, or it is suspected that use or continued use of the product would result in the subject's death. 'Life-threatening' does not mean that had an AE occurred in a more severe form it might have caused death (e.g., hepatitis that resolved without hepatic failure).

B 4 Hospitalisation

Outpatient treatment in an emergency room is not in itself a serious AE, although the reasons for it may be (e.g., bronchospasm, laryngeal oedema). Hospital admissions and/or surgical operations planned before or during a study are not considered AEs if the illness or disease

existed before the subject was enrolled in the study, provided that it did not deteriorate in an unexpected way during the study.

B 5 Important Medical Event or Medical Treatment

Medical and scientific judgement should be exercised in deciding whether a case is serious in situations where important medical events may not be immediately life threatening or result in death, hospitalisation, disability or incapacity but may jeopardize the subject or may require medical treatment to prevent one or more outcomes listed in the definition of serious. These should usually be considered as serious.

Simply stopping the suspect drug does not mean that it is an important medical event; medical judgement must be used.

Examples of such events are:

- Angioedema not severe enough to require intubation but requiring iv hydrocortisone treatment
- Hepatotoxicity caused by paracetamol (acetaminophen) overdose requiring treatment with N-acetylcysteine
- Intensive treatment in an emergency room or at home for allergic bronchospasm
- Blood dyscrasias (e.g., neutropenia or anaemia requiring blood transfusion, etc.) or convulsions that do not result in hospitalisation
- Development of drug dependency or drug abuse

B 6 Intensity Rating Scale:

- 1. Mild (awareness of sign or symptom, but easily tolerated)
- 2. Moderate (discomfort sufficient to cause interference with normal activities)
- 3. Severe (incapacitating, with inability to perform normal activities)

It is important to distinguish between serious and severe AEs. Severity is a measure of intensity whereas seriousness is defined by the criteria in Appendix B 2. An AE of severe intensity need not necessarily be considered serious. For example, nausea that persists for several hours may be considered severe nausea, but not a SAE unless it meets the criteria shown in Appendix B 2. On the other hand, a stroke that results in only a limited degree of disability may be considered a mild stroke but would be a SAE when it satisfies the criteria shown in Appendix B 2.

B 7 A Guide to Interpreting the Causality Question

When making an assessment of causality consider the following factors when deciding if there is a 'reasonable possibility' that an AE may have been caused by the drug.

Time Course. Exposure to suspect drug. Has the subject actually received the suspect drug? Did the AE occur in a reasonable temporal relationship to the administration of the suspect drug?

Consistency with known drug profile. Was the AE consistent with the previous knowledge of the suspect drug (pharmacology and toxicology) or drugs of the same pharmacological class? Or could the AE be anticipated from its pharmacological properties?

De-challenge experience. Did the AE resolve or improve on stopping or reducing the dose of the suspect drug?

No alternative cause. The AE cannot be reasonably explained by another aetiology such as the underlying disease, other drugs, other host or environmental factors.

Re-challenge experience. Did the AE reoccur if the suspected drug was reintroduced after having been stopped? AstraZeneca would not normally recommend or support a re-challenge.

Laboratory tests. A specific laboratory investigation (if performed) has confirmed the relationship.

In difficult cases, other factors could be considered such as:

Is this a recognized feature of overdose of the drug?

Is there a known mechanism?

Causality of 'related' is made if following a review of the relevant data, there is evidence for a 'reasonable possibility' of a causal relationship for the individual case. The expression 'reasonable possibility' of a causal relationship is meant to convey, in general, that there are facts (evidence) or arguments to suggest a causal relationship.

The causality assessment is performed based on the available data including enough information to make an informed judgment. With limited or insufficient information in the case, it is likely that the event(s) will be assessed as 'not related'.

Causal relationship in cases where the disease under study has deteriorated due to lack of effect should be classified as no reasonable possibility.

B 8 Medication Error, Drug Abuse and Drug Misuse

Medication error

For the purposes of this clinical study a medication error is an unintended failure or mistake in the treatment process for an IMP or AstraZeneca NIMP that either causes harm to the participant or has the potential to cause harm to the participant.

A medication error is not lack of efficacy of the drug, but rather a human or process related failure while the drug is in control of the study site staff or participant.

Medication error includes situations where an error:

- occurred
- was identified and intercepted before the participant received the drug
- did not occur, but circumstances were recognized that could have led to an error

Examples of events to be reported in clinical studies as medication errors:

- Drug name confusion
- Dispensing error e.g., medication prepared incorrectly, even if it was not actually given to the participant
- Drug not administered as indicated, for example, wrong route or wrong site of administration
- Drug not taken as indicated e.g., tablet dissolved in water when it should be taken as a solid tablet
- Drug not stored as instructed e.g., kept in the fridge when it should be at room temperature
- Wrong participant received the medication (excluding IWRS errors)
- Wrong drug administered to participant (excluding IWRS errors)

Examples of events that **do not** require reporting as medication errors in clinical studies:

- Errors related to or resulting from IWRS including those which lead to one of the above listed events that would otherwise have been a medication error
- Participant accidentally missed drug dose(s) e.g., forgot to take medication
- Accidental overdose (will be captured as an overdose)
- Participant failed to return unused medication or empty packaging

- Errors related to background and rescue medication, or standard of care medication in open label studies, even if an AZ product
- Medication errors are not regarded as AEs, but AEs may occur as a consequence of the medication error

Drug Abuse

For the purpose of this study, drug abuse is defined as the persistent or sporadic intentional, non-therapeutic excessive use of IMP or AstraZeneca NIMP for a perceived reward or desired non-therapeutic effect.

Any events of drug abuse, with or without associated AEs, are to be captured and forwarded to the Data Entry Site (DES) using the Drug Abuse Report Form. This form should be used both if the drug abuse happened in a study participant or if the drug abuse involves a person not enrolled in the study (such as a relative of the study participant).

Examples of drug abuse include but are not limited to:

- The drug is used with the intent of getting a perceived reward (by the study participant or a person not enrolled in the study)
- The drug in the form of a tablet is crushed and injected or snorted with the intent of getting high

Drug Misuse

Drug misuse is the intentional and inappropriate use (by a study participant) of IMP or AstraZeneca NIMP for medicinal purposes outside of the authorised product information, or for unauthorised IMPs or AstraZeneca NIMPs, outside the intended use as specified in the protocol and includes deliberate administration of the product by the wrong route.

Events of drug misuse, with or without associated AEs, are to be captured and forwarded to the DES using the Drug Misuse Report Form. This form should be used both if the drug misuse happened in a study participant or if the drug misuse regards a person not enrolled in the study (such as a relative of the study participant).

Examples of drug misuse include but are not limited to:

- The drug is used with the intention to cause an effect in another person
- The drug is sold to other people for recreational purposes
- The drug is used to facilitate assault in another person
- The drug is deliberately administered by the wrong route
- The drug is split in half because it is easier to swallow, when it is stated in the protocol that it must be swallowed whole

- Only half the dose is taken because the study participant feels that he/she is feeling better when not taking the whole dose
- Someone who is not enrolled in the study intentionally takes the drug

Appendix C Handling of Human Biological Samples

C 1 Chain of Custody of Biological Samples

A full chain of custody is maintained for all samples throughout their lifecycle.

The Principal Investigator keeps full traceability of collected biological samples from the subjects while in storage at the centre until shipment or disposal (where appropriate).

The sample receiver keeps full traceability of the samples while in storage and during use until used or disposed of or until further shipment and keeps documentation of receipt of arrival.

AstraZeneca will keep oversight of the entire life cycle through internal procedures, monitoring of study sites, auditing or process checks, and contractual requirements of external laboratory providers.

Samples retained for further use will be stored in the AZ-assigned biobanks and will be registered by the AstraZeneca Biobank Team during the entire life cycle.

If required, AstraZeneca will ensure that remaining biological samples are returned to the site according to local regulations or at the end of the retention period, whichever is the sooner.

C 2 Withdrawal of Informed Consent for Donated Biological Samples

If a subject withdraws consent to the use of donated biological samples, the samples will be disposed of/destroyed, and the action documented. If samples are already analyzed, AstraZeneca is not obliged to destroy the results of this research.

As collection of the biological sample(s) is an integral part of the study, then the subject is withdrawn from further study participation.

The Investigator:

- Ensures subjects' withdrawal of informed consent to the use of donated samples is notified immediately to AstraZeneca
- Ensures that biological samples from that subject, if stored at the study site, are immediately identified, disposed of /destroyed, and the action documented

- Ensures the organization(s) holding the samples is/are informed about the withdrawn consent immediately and that samples are disposed of/destroyed, the action documented, and the signed document returned to the study site
- Ensures that the subject and AstraZeneca are informed about the sample disposal

AstraZeneca ensures the organizations holding the samples is/are informed about the withdrawn consent immediately and that samples are disposed of/destroyed and the action documented and returned to the study site.

C 3 International Airline Transportation Association (IATA) 6.2 Guidance Document

LABELLING AND SHIPMENT OF BIOHAZARD SAMPLES

International Airline Transportation Association (IATA) classifies biohazardous agents into 3 categories (https://www.iata.org/whatwedo/cargo/dgr/Documents/infectious-substance-classification-DGR56-en.pdf.). For transport purposes the classification of infectious substances according to risk groups was removed from the Dangerous Goods Regulations in the 46th edition (2005). Infectious substances are now classified either as Category A, Category B or Exempt. There is no direct relationship between Risk Groups and Categories A and B.

Category A Infectious Substances are infectious substances in a form that, when exposure to it occurs, is capable of causing permanent disability, life-threatening or fatal disease in otherwise healthy humans or animals. Category A pathogens are e.g., Ebola, Lassa fever virus:

• are to be packed and shipped in accordance with IATA Instruction 602

Category B Infectious Substances are infectious substances that do not meet the criteria for inclusion in Category A. Category B pathogens are e.g., Hepatitis A, B, C, D, and E viruses, Human immunodeficiency virus types 1 and 2. They are assigned the following UN number and proper shipping name:

- UN 3373 Biological Substance, Category B
- are to be packed in accordance with UN3373 and IATA 650

Exempt - all other materials with minimal risk of containing pathogens

• Clinical trial samples will fall into Category B or exempt under IATA regulations

- Clinical trial samples will routinely be packed and transported at ambient
- Temperature in IATA 650 compliant packaging (https://www.iata.org/whatwedo/cargo/dgr/Documents/infectious-substance-classification-DGR56-en.pdf.)
- Biological samples transported in dry ice require additional dangerous goods specification for the dry-ice content
- IATA compliant courier and packaging materials should be used for packing and transportation and packing should be done by an IATA certified person, as applicable
- Samples routinely transported by road or rail are subject to local regulations which require that they are also packed and transported in a safe and appropriate way to contain any risk of infection or contamination by using approved couriers and packaging/containment materials at all times. The IATA 650 biological sample containment standards are encouraged wherever possible when road or rail transport is used.

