- 2. The subject will be offered follow-up on a monthly basis via telephone calls while continuing eDiary completion (no further procedures will be performed) until the subject completes the EOT visit at Week 52 (+/-5 days). In addition to the PRO assessments that are performed at home, the subject may also complete the other clinic specified PRO assessments (as defined in the SoA 1.1) at home as well.
- 3. If the subject cannot or does not wish to comply with any of the options above, (or any component of them such as only telephone-based visits without completion of the eDiary), the Investigator will only contact the subject at 52 weeks post-randomization. No other study assessments will be performed prior to this contact.

If the subject chooses option 2 or 3, the key information to be collected during the telephone calls are AEs/SAEs, changes in concomitant medication, health care utilization, and COPD exacerbation information.

Subjects who initially choose options 1 or 2 and subsequently cannot or do not wish to comply with the requirements of their option can continue with a less intensive option (i.e., subject initially choosing option 1 can continue with options 2 or 3, subjects initially choosing option 2 can continue with option 3).

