7.3 Withdrawal from the Study

A subject may withdraw from the study (e.g., withdraw consent), at any time (IP and assessments) at his/her own request, without prejudice to further treatment. A subject who considers withdrawing from the study must be informed by the Investigator about modified follow-up options (e.g., telephone contacts, contacts with a relative or treating physician, or information from medical records) as per Section 7.1.1.

A subject who withdraws consent will always be asked about the reason(s) and the presence of any adverse events (AE). The Investigator will follow-up subjects as medically indicated. A withdrawal visit is essential to collect as much data as possible for the subject as per EOT visit described in SoA, Table 2. The subject will return all study supplied equipment including eDiary.

If the subject withdraws consent for disclosure of future information, the sponsor may retain and continue to use any data collected before such a withdrawal of consent.

If a subject withdraws from the study, he/she may request destruction of any samples taken, and the Investigator must document this in the site study records.

If the subject only withdraws consent for the retention of biological samples (blood, nasal, sputum, urine etc.) for future exploratory use (e.g., scientific health-related research), the subject will not be withdrawn from the study.

Withdrawal of consent from the study must be ascertained and documented by the Investigator and recorded in the eCRF as well as in the Informed Consent Form (ICF) or assent form.

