8.8.1 Storage, Re-use and Destruction of Biomarker Samples

All biomarker samples described in Section 8.8 (for example blood, sputum, nasal, and urine samples) will be stored for a maximum of 15 years from the date of the Last Subject's Last Visit, after which they will be destroyed. The results of this biomarker research will not be reported in the CSR but in an addendum, or separately in a scientific report or publication. The results of this biomarker research may be pooled with biomarker data from other studies with the study drug to generate hypotheses to be tested in future research. Any residual biological samples may be retained for up to 15 years and used for the purpose of investigating COPD, the pharmacology of tezepelumab, predictors of response, or assay development. If a subject does not allow samples to be used for future biomarker research

(e.g., scientific health-related research), they may continue with their samples being used for the main study. The results of any future analyses will not be reported in the CSR itself but as an addendum, or separately in a scientific report or publication

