COVID-19 pandemic. Confirmation of subject's re-consent needs to be documented in the source documents.

The ICF will contain a separate section that addresses the use of remaining mandatory samples for optional exploratory research. The Investigator or authorized designee will explain to each subject the objectives of the exploratory research. Subjects will be told that they are free to refuse to participate and may withdraw their consent at any time and for any reason during the storage period. The subject will give a separate agreement to allow any remaining specimens to be used for exploratory research. Subjects who decline to participate in this optional research will indicate this in the ICF. If a subject withdraws consent to the use of donated biological samples, the samples will be disposed of/destroyed, and the action documented. If samples already have been analyzed at the time of the request, AstraZeneca will not be obliged to destroy the results of this research.

A 4 Data Protection

Each subject will be assigned a unique identifier by the sponsor. Any subject records or data sets transferred to the sponsor will contain only the identifier; subject names or any information which would make the subject identifiable will not be transferred.

The subject must be informed that his/her personal study-related data will be used by the sponsor in accordance with local data protection law. The level of disclosure must also be explained to the subject.

The subject must be informed that his/her medical records may be examined by Clinical Quality Assurance auditors or other authorized personnel appointed by the sponsor, by appropriate IRB/IEC members, and by inspectors from regulatory authorities.

A 5 Committees Structure

The safety of all AstraZeneca clinical studies is closely monitored on an on-going basis by AstraZeneca representatives in consultation with Patient Safety. Issues identified will be addressed; for instance, this could involve amendments to the Clinical Study Protocol and letters to Investigators.

A 6 Dissemination of Clinical Study Data

Any results both technical and lay summaries for this trial, will be submitted to EU CTIS within a year from global End of Trial Date in all participating countries, due to scientific reasons, as otherwise statistical analysis is not relevant.

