Subjects may withdraw from this genetic research at any time, independent of any decision concerning participation in other aspects of the main study. Voluntary withdrawal will not prejudice further treatment. Procedures for withdrawal are outlined in Section 7.3 of the main Clinical Study Protocol.

Collection of samples for genetic research

Blood samples for genetic research will be obtained from subjects at randomization visit. Although DNA is stable, early sample collection is preferred to avoid introducing bias through excluding subjects who may withdraw due to an adverse event (AE), such subjects would be important to include in any genetic analysis. If for any reason the sample is not drawn at randomization visit, it may be taken at any visit until the last study visit. Only one sample should be collected per subject for genetics during the study. Samples will be collected, labelled, stored, and shipped as detailed in the Laboratory Manual.

Coding and storage of DNA samples

The processes adopted for the coding and storage of samples for genetic analysis are important to maintain subject confidentiality. Samples will be stored for a maximum of 15 years, from the date of last subject last visit, after which they will be destroyed. DNA is a finite resource that is used up during analyses. Samples will be stored and used until no further analyses are possible or the maximum storage time has been reached.

An additional second code will be assigned to the blood either before or at the time of DNA extraction replacing the information on the sample tube. Thereafter, the sample will be identifiable only by the second, unique number. This number is used to identify the sample and corresponding data at the AstraZeneca genetics laboratories, or at the designated organization. No personal details identifying the individual will be available to any person (AstraZeneca employee or designated organizations working with the DNA).

The link between the subject enrolment/randomization code and the second number will be maintained and stored in a secure environment, with restricted access at AstraZeneca or designated organizations. The link will be used to identify the relevant DNA samples for

analysis, facilitate correlation of genotypic results with clinical data, allow regulatory audit, and permit tracing of samples for destruction in the case of withdrawal of consent.

Ethical and regulatory requirements

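### Appendix C 2 withdraws from the study, without exception, anyone who withdraws consent to use of donated samples; for exploratory-only or future-use withdrawal this contradicts sections 7.3 and 8.8.1 and Appendices A 3 and D 2

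*Protocol*

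**What the plan says.** Five places in the protocol address withdrawal of consent for samples.

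- **Appendix C 2** opens with the same sentence that stands in Appendix A 3: "If a subject withdraws consent to the use of donated biological samples, the samples will be disposed of/destroyed, and the action documented". It then adds a consequence for the whole study: "As collection of the biological sample(s) is an integral part of the study, then the subject is withdrawn from further study participation". It does not separate mandatory samples from exploratory ones, and it points to no other section.
- **Section 7.3** has a narrower trigger, "If the subject only withdraws consent for the retention of biological samples (blood, nasal, sputum, urine etc.) for future exploratory use", and the opposite outcome: "the subject will not be withdrawn from the study".
- **Section 8.8.1** says of subjects who do not allow future biomarker research that "they may continue with their samples being used for the main study".
- **Appendix A 3** uses the shared sentence for optional research on remaining specimens. Subjects are told they may refuse it or leave it at any time. No study withdrawal follows.
- **Appendix D 2** says of the optional DNA sample: "Subjects may withdraw from this genetic research at any time, independent of any decision concerning participation in other aspects of the main study".

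Section 7.3 also requires the investigator to tell a subject who is considering withdrawal about modified follow-up, such as telephone contact, contact with a relative or treating physician, or medical records. C 2 does not mention this step.

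**The concern.** A subject tells the site that stored samples may no longer be used for exploratory research. A coordinator who opens section 7.3 keeps the subject in the study. One who opens Appendix C, whose title covers the handling of human biological samples, withdraws the subject.

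Under the second reading the trial loses data that it wants. The primary estimand (protocol 9.2.1) uses all available data to Week 52, on or off treatment. The synopsis relies on that when it declines to adjust the number randomized for evaluability. Study withdrawal ends exacerbation follow-up at the point where events can no longer be assessed (protocol 9.4.2.1, SAP 3.2.1.1). It also sets the exacerbation-free response to 0 if Visit 16 is not completed (SAP 3.2.2.2), and makes the subject an SGRQ non-responder if the Week 52 score is missing (SAP 3.2.2.6).

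There is a consent issue too. Appendix A 3 presents the exploratory research as freely refusable, while C 2 read literally makes loss of study participation the price of withdrawing from it.

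**Working it through.** **Step 1: the passages by type of request.**

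| What the subject withdraws | C 2 read literally | Other sections | Conflict? |
|---|---|---|---|
| Retention for future exploratory use only | Withdrawn from study | 7.3: stays in | Yes |
| Future biomarker research | Withdrawn | 8.8.1: may continue, main-study use goes on | Yes |
| Optional research on remaining mandatory specimens | Withdrawn | A 3: disposal, no study withdrawal attached | Yes |
| Optional genetic sample | Withdrawn | D 2: independent of main study | Yes |
| Use of mandatory main-study samples | Withdrawn | 7.3 and 8.8.1 do not address it | No |

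The conflict is confined to the first four rows.

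**Step 2: can C 2 be read as limited to mandatory samples?** Its stated reason, that collection is integral to the study, points that way. Its trigger does not: the opening sentence is the one A 3 applies to optional research. C 2 then speaks of the results of this research although C 2 itself names none; in A 3 the same phrase refers to the exploratory research. A site cannot find the limit in the text.

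**Step 3: size.** The documents give no rate for such requests, so the power effect can only be shown over an assumed range.

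Inputs (protocol 9.2): one-sided alpha 5%, rate ratio 0.70, dispersion k = 0.6, 10% uniform drop-out, placebo rate 1.6 (original) or 1.2 (updated). Under uniform drop-out a drop-out loses half the follow-up on average, so mean exposure is t = 1 − 0.10 × 0.5 = 0.95.

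Formula: n per arm = (z0.95 + z0.80)² × [1/(λ0 t) + 1/(λ1 t) + 2k] / (ln RR)².

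Reproducing the plan's figure at rate 1.6:
- λ0 t = 1.6 × 0.95 = 1.52 and λ1 t = 1.12 × 0.95 = 1.064.
- Bracket = 0.658 + 0.940 + 1.2 = 2.798.
- n = 6.183 × 2.798 / 0.1272 = 136.0. The plan states 136 without the futility look.
- With 141 per arm the power is 81.25%. The plan states 81.2%.

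At the updated 169 per arm and rate 1.2, power before the futility loss is 81.49%. Now let an extra share x of subjects be withdrawn at uniform times, so that t = 0.95 × (1 − 0.5x):

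| x (assumed) | t | Power, 169 per arm |
|---|---|---|
| 0 | 0.950 | 81.49% |
| 1% | 0.945 | 81.38% |
| 2% | 0.941 | 81.27% |
| 5% | 0.926 | 80.93% |
| 10% | 0.903 | 80.35% |

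Even an extra 10% costs only about 1.1 percentage points (81.49 − 80.35 = 1.14).

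**The case against.** The strongest reply is that the passages can be read together. C 2 is the general rule for samples the study needs, and section 7.3, with its word only, is the specific exception. Section 8.8.1 presupposes that main-study use continues. On that reading nothing contradicts C 2 for a subject who refuses mandatory samples. This stands, and it limits the point. A reader might infer that 7.3 and 8.8.1 keep in the study everyone who withdraws consent to donated samples. Those sections do not say so.

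A reader might also infer that the reason given in C 2 is simply wrong, because exacerbation counting needs no sample and section 7.1.1 keeps some subjects to Week 52 by telephone, "while continuing eDiary completion (no further procedures will be performed) until the subject completes the EOT visit". That goes too far. Those options are for subjects who have stopped investigational product. PK and anti-drug antibodies are secondary objectives, and safety laboratory tests are scheduled during treatment. The documents do not show that mandatory sampling is dispensable for a subject still being dosed.

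Two further replies have weight. Several optional collections carry their own rules (D 2 for DNA; a separate consent addendum for sputum and nasal samples), so a careful site may reach the right answer. And a withdrawn subject is not lost altogether: he or she stays in the full analysis set and contributes events and time at risk up to withdrawal, later time is covered by the missing-data analyses in SAP Appendix 8.2, and section 7.3 requires modified follow-up to be discussed.

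What remains is that the exception is not written into C 2, and that C 2 shares its trigger with the passage on optional research.

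**Conclusion.** The contradiction holds for subjects who withdraw consent only for retention or for exploratory or future use, including remaining specimens under A 3 and the genetic sample under D 2. For them, C 2 read literally orders a study withdrawal that the rest of the protocol rules out or does not attach, and needlessly ends follow-up that the primary estimand is meant to use. It does not hold for subjects who refuse samples integral to the main study.

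The number affected is unknown, and depends on how often the request arises and which passage the site follows. The power table rests on an assumed rate and on uniform timing. Within that range the loss is 0.1 to 0.2 percentage points for 1% to 2% extra withdrawals. A reader might infer a threat to the sample size, but the figures do not support one. No alpha, estimand or analysis changes. The case for acting is conflicting site instructions, avoidable missing data and a consent promise that C 2 undercuts.

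**What to change.** Reconcile the passages by amending Appendix C 2:

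1. Limit the study-withdrawal sentence to withdrawal of consent for samples integral to the main study.
2. State that withdrawal confined to retention, exploratory or future use leads to disposal of the samples it covers, that main-study use is unaffected as in 8.8.1, and that the subject remains in the study.
3. Cross-refer to 7.3, 8.8.1, A 3 and D 2.
4. Point to the modified follow-up options that 7.3 already requires to be discussed before a subject withdraws.

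How to handle a subject who refuses mandatory main-study samples, including any question of continued dosing, is for the sponsor to decide. A blanket sentence keeping every such subject in the study would go beyond reconciliation.

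The cost is a few sentences in one appendix, with no added procedures, subjects or analyses.
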